7.2 Pooling Across Trial Sites

All data from all sites will be pooled for analysis. Study site will be ignored in the primary analysis of the primary endpoint but will be included as a covariate in a planned covariate-adjusted secondary analysis.

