3.2 Secondary Objectives

The trial will also evaluate the HCQ and AZM hypotheses using the following secondary endpoints:

- Mortality during the index hospitalization
- Number of days on mechanical ventilation during the index hospitalization
- Progression to mechanical ventilation during index hospitalization
- World Health Organization ordinal scale on day 28
- Days from randomization until hospital discharge
- Duration of fever after randomization
- Duration of supplemental oxygen use after randomization

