6 DESCRIPTION OF EFFICACY ENDPOINTS

6.1 Primary Endpoint

The primary outcome measure is the World Health Organization (WHO) ordinal scale for clinical improvement as measured on day 14 after randomization. The WHO scale has 9 levels numbered 0 to 8 with 0 denoting no clinical or virologic evidence of infection and 8 denoting death.

Table 2. World Health Organization ordinal scale for clinical improvement

Descriptor	Score
No clinical or virologic evidence of infection	0
No limitation of activities	1
Limitation of activities	2
Hospitalized, no oxygen therapy	3
Oxygen by mask or nasal cannula	4
Non-invasive ventilation or high-flow oxygen	5
Intubation and mechanical ventilation	6
Mechanical ventilation + additional organ support (pressors, renal replacement therapy, ECMO)	7
Death	8

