8.5 Secondary Analyses of the Primary Endpoint

The primary analysis is unadjusted for baseline covariates but a covariate-adjusted analysis will also be presented for the major hypotheses in order to target a potentially more clinically relevant treatment effect estimand. Baseline covariates for this analysis will include ventilator status at the time of

randomization and enrolling site. To implement the covariate-adjusted analysis, baseline ventilator status and site will be included as main effects covariate adjustments in the proportion odds model along with the set of treatment group indicators used in the primary analysis. Win ratios for HCQ and AZM will be defined in a manner analogous to the primary analysis. The covariate-adjusted win ratio for HCQ will be a comparison between a hypothetical randomly selected patient from one of the HCQ groups (2, 4, or 6) and a hypothetical randomly selected patient from the same site, same baseline ventilator status, and same AZM subgroup who was randomized to no HCQ. The covariate-adjusted win ratio for AZM will be a comparison between a hypothetical randomly selected patient from one of the AZM groups (3 or 4) and a hypothetical randomly selected patient from the same site, same baseline ventilator status, and same HCQ subgroup who was randomized to no AZM.

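### The covariate-adjusted analysis uses ventilator status in place of the starting WHO level, treating non-ventilated patients at levels 3, 4 and 5 as alike and pulling its effect estimate toward the null

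*SAP*

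**What the plan says.** The SAP keeps covariates out of the main analysis: "The primary analysis is unadjusted for baseline covariates" (Section 8.5). A secondary, adjusted version is planned. Section 7.2 names only site for it, which "will be included as a covariate in a planned covariate-adjusted secondary analysis"; Section 8.5 gives the full list, namely that "baseline ventilator status and site will be included as main effects covariate adjustments in the proportion odds model".

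For HCQ, the adjusted win ratio compares a treated patient with one from the "same site, same baseline ventilator status, and same AZM subgroup who was randomized to no HCQ". The AZM version is defined in the same way within HCQ subgroup. The stated reason for the analysis is "in order to target a potentially more clinically relevant treatment effect estimand"; precision is not mentioned.

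Table 2 in Section 6.1 separates three states short of intubation for a patient in hospital: no oxygen (3), mask or nasal cannula (4), and "Non-invasive ventilation or high-flow oxygen" (5). The baseline value of this scale is not a covariate anywhere in the SAP.

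**The concern.** Section 3 enrols hospitalized patients, so everyone starts at level 3 or above. Ventilator yes/no splits levels 6-7 from the rest and merges levels 3, 4 and 5. The matched pairs of Section 8.5 can therefore set a patient on no oxygen against one on high-flow oxygen and count them as having the same baseline. That sits poorly with an analysis whose declared purpose is a more clinically relevant comparison.

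There is also a statistical cost. The starting level of an ordinal severity scale plausibly predicts the same scale two weeks later. The odds ratio in a proportional odds model is non-collapsible: omitting a prognostic covariate moves the estimate toward 1 even when the arms are perfectly balanced. The adjusted analysis would then show a smaller effect, and a lower posterior probability of benefit or harm, than an analysis within starting level.

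**Working it through.** The SAP states no figure that depends on this choice, so there is nothing to reproduce. The check has two parts.

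**1. How alike are the matched pairs?** Assume baseline levels 3/4/5/6-7 at 30/50/10/10% or 20/40/20/20%. The chance that two random non-ventilated patients differ in level is 1 minus the sum of squared shares.

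- First mix: 1 − [(30/90)² + (50/90)² + (10/90)²] = 1 − (0.111 + 0.309 + 0.012) = 0.57.
- Second mix: 1 − [(20/80)² + (40/80)² + (20/80)²] = 1 − (0.0625 + 0.25 + 0.0625) = 0.63.

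Under these mixes, more than half of such pairs would not share a starting level.

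**2. What does it cost?** From the SAP: a nine-level outcome and a proportional odds model (Section 8.3). The number 500 appears in Section 11.1 for the monitoring simulation and serves here only as an illustrative sample size.

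Assumed, because the SAP does not give them:

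- the two mixes above
- a conditional odds ratio of 1.5 (log 0.405)
- an underlying day-14 distribution over levels 0 to 8 of 5/20/25/12/12/6/5/5/10%
- log-odds of a worse outcome for levels 4, 5 and 6-7 against level 3 of 0.4, 1.0, 2.0 (weak); 0.7, 1.7, 2.6 (middle); 1.0, 2.4, 3.2 (strong)

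The models were fitted by maximum likelihood to expected cell frequencies in two equal arms, with flat priors and no site term. Gain in effective sample size = (z of the finer model / z of the ventilator model)², where z = log odds ratio / SE. 'Three groups' means no oxygen, any oxygen or non-invasive support, and ventilated.

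| Mix, prognosis | Ventilator: log OR (SE) | Three groups: log OR (SE) | Four levels: log OR (SE) | Gain, three groups | Gain, four levels |
|---|---|---|---|---|---|
| 30/50/10/10, weak | 0.399 (0.1587) | 0.403 (0.1588) | 0.405 (0.1589) | 1.018 | 1.030 |
| 30/50/10/10, middle | 0.388 (0.1588) | 0.399 (0.1591) | 0.405 (0.1593) | 1.054 | 1.087 |
| 30/50/10/10, strong | 0.373 (0.1590) | 0.393 (0.1596) | 0.405 (0.1599) | 1.105 | 1.171 |
| 20/40/20/20, weak | 0.397 (0.1588) | 0.402 (0.1589) | 0.405 (0.1590) | 1.019 | 1.038 |
| 20/40/20/20, middle | 0.384 (0.1588) | 0.395 (0.1591) | 0.405 (0.1594) | 1.055 | 1.108 |
| 20/40/20/20, strong | 0.366 (0.1589) | 0.386 (0.1595) | 0.405 (0.1599) | 1.104 | 1.213 |

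Last row: z is 2.302 with ventilator status and 2.535 with four levels; (2.535/2.302)² = 1.213. A second assumed outcome distribution (10/15/25/10/12/6/6/4/12%) changed no ratio by more than 0.003.

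The SE is the same or slightly larger with the finer covariate. The whole gain comes from the estimate, which moves from 0.366-0.399 to 0.405.

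**Sensitivity.** With equal log-odds steps between adjacent levels and three other mixes (20/50/15/15, 30/55/10/5 and 15/35/25/25%), the four-level gain is 0 at no step, 3-4% at 0.5, 13-14% at 1.0 and 28-30% at 1.5. Using a two-sided 5% test only as a yardstick, power rises from 0.71 to 0.73, from 0.67 to 0.72, and from about 0.60 to 0.70 at the three non-zero steps.

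**The case against.** Section 8.5 is coherent as written. Ventilator status is the randomization stratifier (Section 4), site is a natural second covariate, both are pre-specified, and pairs matched on them define a complete estimand. A finer match is a different estimand, not the correction of an error. This stands, and it is why the point is an improvement to a supportive analysis. It does not remove the mismatch with the section's own stated purpose.

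Three stronger readings are tempting, and the documents do not support them.

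- A reader might infer that precision is lost and the credible intervals widen. The SEs above show otherwise: on the log-odds scale, the finer covariate leaves the interval the same or marginally wider. The loss is attenuation and lower power.
- A reader might infer that the four-level baseline is available from data the trial needs anyway. The secondary endpoint "Duration of supplemental oxygen use after randomization" needs only on/off times for oxygen. With ventilator status, that gives no oxygen, any oxygen and ventilated; it does not separate mask or cannula from high-flow or non-invasive support. The SAP does not show whether the device, or a baseline WHO score, is recorded.
- A reader might take the gain as patients lost to the trial. The primary analysis has no covariates and is untouched, and Section 11 bases interim monitoring on the methods of Section 8 without calling for the adjusted version.

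The SAP also does not say whether ventilator status counts non-invasive ventilation. If it does, part of level 5 is separated, but patients on no oxygen and on high-flow oxygen still share a category.

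**Conclusion.** The point holds as a minor, low-cost improvement to the covariate-adjusted secondary analysis. Matching on ventilator status treats levels 3, 4 and 5 as one baseline state, which pulls the adjusted effect toward the null and lowers the chance of a clear posterior statement. Against ventilator status alone, the effective sample size would rise by about 3% to 21% with four levels and about 2% to 10% with three groups.

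These figures rest on assumed baseline mixes, prognostic strengths and outcome distribution, an odds ratio of 1.5 and 500 patients. The calculation also leaves out the six-group structure, site and the informative priors of Section 8.4. If the starting level had no prognostic value there would be no gain; with stronger prognosis than in the main table, the gain could approach 30%. The direction is secure wherever the starting level predicts outcome; the size is not known from the SAP.

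**What to change.** In Section 8.5, replace baseline ventilator status by the WHO level at randomization as a factor with levels 3, 4, 5 and 6-7. This factor contains the ventilator stratifier if ventilator status means levels 6-7, which the section should state. If the oxygen device at randomization is not recorded, use no oxygen, oxygen or non-invasive support, and ventilated. Keep site, as in Section 7.2. Define the adjusted win ratios for HCQ and AZM for pairs with the same baseline level, the same site and the same subgroup of the other drug.

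The cost is SAP wording, two more parameters (one with the three-group version) and deriving the baseline level for every participant. The change should be made before outcomes by arm are seen, so that the covariate is not chosen post hoc. The unadjusted primary analysis stays as it is.

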7.3 Withdrawals, Dropouts, Loss to Follow-up

All patients and all data will be included in the analyses. Patients who withdraw from the study or are lost to follow-up before collection of the primary endpoint will be analyzed using their last available follow-up data according to the imputation rules described in Section 7.1. Participants with no analyzable follow-up data for any safety or efficacy endpoints will be excluded and will not appear in tabulations of baseline data. The number of such exclusions, if any, will be reported.

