3 STUDY DESIGN AND OBJECTIVES

PROTECT is an open-label, factorial randomized clinical trial with two factors and nested randomization. Patients hospitalized with confirmed SARS-CoV-2 infection will be initially randomized to one of two arms in a 1:1 ratio: 1) Standard of care treatment or 2) Standard of care treatment plus 5 days of hydroxychloroquine (HCQ). Patients with no contraindication to azithromycin (AZM) who have not received AZM in the seven days prior to enrollment will undergo a second randomization in a 1:1 ratio to either receive 1) No AZM or 2) 5 days of AZM. The resulting treatment group combinations are summarized in Table 1. Participants will be followed for 28 days after randomization or until hospital discharge, whichever is later. The primary endpoint is the World Health Organization (WHO) ordinal scale for clinical improvement as measured on day 14 after randomization (see Section 6.1 for details).

Table 1. Treatment groups

	AZM: No	AZM: Yes	AZM: Not Eligible
HCQ: No	Group 1: SOC	Group 3: SOC + AZM	Group 5: SOC, AZM-ineligible
HCQ: Yes	Group 2: SOC + HCQ	Group 4: SOC + HCQ + AZM	Group 6: SOC + HCQ, AZM-ineligible

HCQ = hydroxychloroquine, AZM = azithromycin, SOC = standard of care

Hypothesis #1 (HCQ versus no HCQ): Groups 2+4+6 versus 1+3+5

Hypothesis #2 (AZM versus no AZM): Groups 3+4 versus 1+2

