5 POPULATIONS FOR EFFICACY AND SAFETY ANALYSES

5.1 Intention-to-treat population

The intention-to-treat (ITT) population will include all participants who receive a randomized treatment assignment, including those who are later determined not to meet trial eligibility criteria, unless the randomization was an unintentional administrative error, as determined by the coordinating center at the Duke Office of Clinical Research. Patients will be assigned to treatment groups based on each patient's randomized treatment group assignment regardless of which treatment if any the patient actually received.

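### SAP 7.3 and 5.1 let some randomized patients leave the baseline table or the ITT population of an open-label trial without a count by group or a safeguard on the decision (minor)

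*SAP*

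**What the plan says.** SAP section 3 describes the design: "PROTECT is an open-label, factorial randomized clinical trial with two factors and nested randomization". The assignment is therefore known once it is made.

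Section 5.1 says that the ITT population "will include all participants who receive a randomized treatment assignment, including those who are later determined not to meet trial eligibility criteria". It allows one exception: "unless the randomization was an unintentional administrative error, as determined by the coordinating center". It states no criteria, timing, masking or count for that exception.

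Section 7.3 opens with "All patients and all data will be included in the analyses". Patients who withdraw or are lost before the primary endpoint "will be analyzed using their last available follow-up data according to the imputation rules described in Section 7.1". The section then says that those without analyzable follow-up on any endpoint, whether safety or efficacy, "will be excluded and will not appear in tabulations of baseline data". The next sentence is "The number of such exclusions, if any, will be reported". Neither treatment group nor reason is mentioned.

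**The concern.** Having no outcome can justify a patient's absence from an outcome model. It does not justify absence from the baseline table, which needs only data from before assignment. The baseline table is where a reader checks that the groups were comparable as randomized. If it is built on retained patients, it describes a population partly selected after an open assignment.

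Willingness to stay may depend on the allocation. Patients in groups 1 and 5 receive no study drug and might leave at once more often than the others. A single total would not show this.

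The exception in 5.1 raises a related but separate issue, because it changes the primary analysis population itself. When assignments are known and nothing limits what the coordinating center may consider, the plan gives a reader no means of confirming that removals were unrelated to arm or outcome.

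**Working it through.** The SAP gives no dropout rate and no figure on this point, so there is nothing to reproduce. The check compares the texts and then gives two illustrations on stated assumptions.

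**1. The texts side by side**

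| Question | 5.1 | 7.3 |
|---|---|---|
| Who is kept | Everyone randomized, ineligible patients included | Everyone (opening sentence) |
| Who is removed | Administrative-error randomizations | Patients with no analyzable safety or efficacy data |
| Removed from | ITT population | Analyses and baseline tables |
| Basis for the decision | Coordinating center's judgement, no criteria or masking stated | Absence of data |
| Reporting promised | None stated | A number, not by group |

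The 7.3 exclusion is not among the exceptions in 5.1, so the two sections define different populations. Section 10 shows that the SAP specifies counts by group when it intends them: study drug discontinuation is tabulated overall and by treatment group. Section 4 shows that the baseline facts needed exist for every randomized patient, since azithromycin eligibility and ventilator status both stratify the randomization.

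**2. What a split by arm shows that a total does not**

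Assume 500 patients (the number in the section 11.1 simulation), a 1:1 comparison, and exclusions unrelated to arm. The two-sided probability of at least r of T exclusions on one side is 2 × P(Bin(T, 0.5) ≥ r).

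- T = 10 (2% of 500), all on one side: 2 × 0.5^10 = 0.002.
- T = 10, at least 8 on one side: 2 × (45 + 10 + 1)/1024 = 0.11.
- T = 15 (3%), at least 12 on one side: 2 × (455 + 105 + 15 + 1)/32768 = 0.035.

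A bare total of 10 or 15 cannot separate any of these from an even split.

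**3. How far one-sided loss could move the win ratio**

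Assume no true effect and a day 14 WHO distribution for scores 0 to 8 of 5, 25, 25, 8, 10, 7, 6, 4 and 10%. Let a fraction d of the control side be lost, all from one part of the scale. By the section 8.2 formula, the win probability without loss is (1 − Σp²)/2 = (1 − 0.164)/2 = 0.418. After the loss,

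win ratio = (0.418 − d·a)/(0.418 − d·b),

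where a is the probability that a treated patient does better than a lost one, and b that he or she does worse.

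- Loss from scores 0–2: a = 0.159, b = 0.609. At d = 2%, 0.4148/0.4058 = 1.02; at d = 5%, 0.4100/0.3875 = 1.06.
- Loss from scores 6–8: a = 0.862, b = 0.062. At d = 2%, 0.4008/0.4168 = 0.96; at d = 5%, 0.3749/0.4149 = 0.90.

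These are extreme cases. At 1–2% loss the shift is at most about 0.04. A one-sided 5% loss of severe patients would bring the win ratio to about the 0.9 used to define moderate harm in Table 5. Listing the lost patients in the baseline table would not change these values, because they have no outcome either way. It would show that the loss had occurred, and where.

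**The case against.** The strongest reply is that the rule in 7.3 is very narrow. Patients are in hospital, safety data are collected from randomization (section 10), a WHO assessment within 21 days can stand in for day 14 (section 7.1), and any usable datum keeps a patient in. The SAP also expects missing data to be rare. This stands, and it is why the point is minor.

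It can also be said that 7.3 is a general rule followed by an exception. That is a fair reading within 7.3, but it leaves the conflict with 5.1.

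Section 7.1 allows the missing-data approach to be revised if more than 2% of patients have no assessment within 14 ± 6 days. That is some protection. But the revision is optional, the trigger is not by arm, and the SAP does not say whether patients excluded under 7.3 count towards it.

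Four stronger readings are tempting, and the document does not support them:

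- *That the losses cannot be seen or checked.* A number is promised, and nothing forbids a split by group. The SAP simply does not commit to one.
- *That the comparator is standard of care alone.* This is true only of groups 1 and 5. Group 3, on the no-HCQ side, receives azithromycin; group 2, on the no-AZM side, receives hydroxychloroquine.
- *That administrative errors are judged unblinded.* The SAP is silent on masking. The protocol, not at hand, may say more.
- *That a bias of about 2 percentage points follows.* Assume 250 per side, 55% discharged, and immediate loss of 4% without drug and 1% with drug, all of whom would have been discharged. The no-drug side becomes (137.5 − 10)/240 = 53.1%. A gap of nearly 2 points appears only if the drug side is held at 55.0%. Treated alike, it becomes (137.5 − 2.5)/247.5 = 54.5%, a gap of 1.4 points. It would be smaller for HCQ, because group 3 receives a drug. The rates are all assumed, and the 7.3 change would not alter the gap.

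**Conclusion.** The point holds as a minor one. Section 7.3 removes some randomized patients from the baseline tables, against its own first sentence and against 5.1, and commits only to a number. Section 5.1 permits removals from the primary population without tying them to pre-randomization facts, masking the decision or counting them.

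No size can be read from the SAP, and the affected group is probably small. For 7.3 the consequence is lost transparency about allocation-related loss; no biased estimate is demonstrated that the change would correct. For 5.1 the consequence is an unguarded route to selective removal; nothing in the document suggests it has been or would be misused. The illustrations rest on the assumed 500 patients, loss rates and WHO distribution.

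**What to change.** - **Section 7.3:** tabulate baseline data for all ITT patients as randomized. Report patients without analyzable follow-up by each of the six groups, with their baseline ventilator status. Reword the opening sentence so that it agrees with what follows and with 5.1.
- **Section 5.1:** allow an administrative-error exclusion only on facts present before randomization, decided without access to assignment or outcome. List these exclusions by group with the reason.

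The cost is SAP wording. Ventilator status and azithromycin eligibility are already known at randomization, and no planned model changes.

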8 ANALYSIS OF THE PRIMARY ENDPOINT

8.1 Parametric Win Ratio Analysis

The primary endpoint analysis will focus on assessing the overall effects of standard of care plus HCQ versus no HCQ (Hypothesis #1) and AZM versus no AZM (Hypothesis #2), as detailed in Section 3.1. Analysis will be performed in the intention-to-treat (ITT) population, as defined in Section 3.1. The analytic approach will be a model-based parametric implementation of the win ratio framework. [1] In a conventional win ratio analysis, the win ratio statistic is calculated by forming all possible pairs of 1 participant from the treatment group and 1 participant from the control group and then dividing the proportion of pairs for which the treated patient has a better outcome by the proportion of pairs for which the untreated patient has a better outcome. The PROTECT trial analysis will estimate this same underlying win ratio quantity but will do so parametrically using a statistical model. The parametric approach was chosen because it facilitates analysis in a Bayesian statistical framework using a range of Bayesian prior distributions. A Bayesian nonparametric implementation of the win ratio with a non-informative prior distribution was tested in simulations prior to trial launch and was found to be anti-conservative in the sense that the prior distribution assigned high prior probability to the hypothesis of large or small win ratio and this led to high probability of a spurious signal during interim analyses. The underlying quantities to be estimated in this analysis are as follows:

Win Ratio for Hypothesis #1 (HCQ versus no HCQ): The win ratio for HCQ versus no HCQ is defined as the probability that a randomly selected patient who was randomized to HCQ has a better outcome than a randomly selected patient from the same AZM subgroup who was randomized to no HCQ divided by the probability that a randomly selected patient who was randomized to HCQ has a worse outcome than a randomly selected patient from the same AZM subgroup who was randomized to no HCQ.

Win Ratio for Hypothesis #2 (AZM versus no AZM): The win ratio for AZM versus no AZM is defined as the probability that a randomly selected patient who was randomized to AZM has a better outcome than a randomly selected patient from the same HCQ subgroup who was randomized to no AZM divided by the probability that a randomly selected patient who was randomized to AZM has a worse outcome than a randomly selected patient from the same HCQ subgroup who was randomized to no AZM.

